Study of Postural Stability in Subjects with Myelopathy using a Portable Virtual Reality Balance Protocol

NCT03810781

Principal Investigator: [name]

Version Date: 9/5/19

Abstract

Veterans are at heightened risk of developing cervical spondylotic myelopathy (CSM) from rigors of military service. Diagnosis of CSM involves a set of clinical findings and is confirmed by imaging the spine.

Gait impairment and disturbances of stance control are hallmarks of CSM and are a consequence of abnormalities in proprioception due to dorsal column tract damage of the spine. Currently, gait and balance deficits rely on clinical level assessments and judgement for detection. An objective measure of posturography has the benefit of: a) quantifying balance-related disability in CSM, b) facilitating structure-functional assessments in CSM, and c) quantifying the degree surgical interventions affect posturography and recovery of function in CSM.

Objective and sensitive means for assessing balance and posturography exist, but are not routinely incorporated in diagnosis or functional tracking of progress after interventions such as surgery. A barrier may be accessibility of posturography and ease of assessments. The Virtual Environment TBI Screen (VETS) was devised using Army Rapid Innovation Development funding to objectively assess balance and posturography in a cost effective, but sensitive manner. VETS involves virtual environments and computerized posturography and is proving to be a sensitive system facilitating diagnosis, treatment, and mitigation of balance dysfunction associated with mTBI.

Our working hypothesis is VETS testing will enhance clinical judgements regarding CSM. This study is designed to provide data critical to a more extensive program of research incorporating posturography into treatment and rehabilitation of CSM. First, a limited comparative study of standing balance will be conducted of 20 veterans being evaluated for cervical spine surgery to treat CSM and 20 otherwise healthy veterans. Second, posturography of the 20 veterans undergoing surgery to treat CSM will be tracked during their scheduled follow up visits to determine the degree VETS scores are affected by surgery and to track recovery from CSM.

List of Abbreviations

ALS	amyotrophic lateral sclerosis
ANOVA	analysis of variance
AUC	area under the curve
COP	center of pressure
CSM	cervical spondylotic myelopathy
CT	computed tomography
DYN	Dynamic
EC	Eyes Closed
EO	Eyes Open

2.0 Introduction

Cervical Spondylotic Myelopathy (CSM), also known as degenerative cervical myelopathy, encapsulates a cascade of events leading to significant degenerative changes in discs, formation of osteophytes, facet hypertrophy, calcification of the posterior longitudinal ligament and ligamentous flavum with resultant canal stenosis and segmental instability ^{1,2}. Progressive impingement on tracts, nerve roots, and neurons may be confined to the cervical spinal cord or may be co-occurring in many locations throughout the spinal column.

In civilians, CSM reflects ‘wear and tear’ presenting generally in aging (> 50 year of age) and more often in males ³. Incidence is estimated at 4.1/100,000 person years in North America ⁴. Veterans are at greater risk for CSM owing to the rigors of military service (heavy axial loading, repeated vigorous activities, and direct trauma to the spine) ^{5,6}. Although there are no agreed upon rates, degenerative disc disease is highly incident in military personnel and is responsible for lost duty time and medical evacuation from forward deployment ⁶. Using Medical Research Surveillance Reports (MRSR) as a guide, incidence of cervical spondylosis is estimated at 150/100,000 person years for 2009 ⁷. Although not specifically reported, incidence rates may be inferred to hold steady or slightly increase over the next surveillance period ⁸. Tracking incidence of CSM from military service to veterans is difficult given the lack of an agreed upon criteria and absence of distinct pathognomonic findings ⁹. However, it is reasonable to assume military experiences initiating degenerative processes would compound that of aging, which is the single most important risk factor in civilians ¹⁰.

Three areas are critical for early identification and management of CSM: detection and diagnosis ⁵, differential diagnosis ¹¹, and functional tracking of signs and symptoms.

Detection and Diagnosis. Given the progressive nature of the disorder, timely identification and treatment is paramount ³. Imaging of the cervical spine and notation of abnormalities alone is insufficient for diagnosis of CSM. Diagnosis of CSM involves a set of clinical findings which are confirmed by magnetic resonance imaging (MRI) and computerized tomography (CT) ^{12, 13}. The most common symptoms of CSM are: numb or clumsy hands, impaired gait, neck and leg stiffness, sensory disturbances in the arms or legs, atrophy of the hand musculature, and sensory loss. Signs of CSM are hyperreflexia, atrophy of intrinsic hand muscles, motor deficits, a broad-based, unstable gait, and bowel and bladder dysfunction. Both sets have considerable variability in presentation depending on cervical level and the degree and severity of impingement. Current tools to assess severity of functional impairment in CSM are the Nurick Scale ^{14, 15} for mobility, Neck Disability Index (NDI)¹⁶ and the modified Japanese Orthopaedic Association (mJOA) scale ¹⁷, which provide a means for a standardized clinical scoring of dysfunction in broad strokes.

Differential Diagnosis. Differential diagnosis is challenging because there is a lack of a definitive finding or biomarker, and signs and symptoms overlap with a number of pathological sensorimotor conditions ^{5, 11}. The most common are multiple sclerosis (MS), amyotrophic lateral sclerosis (ALS), vitamin B12 deficiency and syringomyelia ¹¹. Differential diagnosis requires a host of invasive and noninvasive tests adding time, expense, and discomfort.

Treatment. Alleviation of impingement is typically surgical to decompress and stabilize the affected region ¹⁰. There is considerable debate concerning the efficacy of surgical and nonsurgical interventions, the best type of surgical intervention, as well as the efficacy of combination approaches ^{3, 18-21}. With the available outcome measures (mJOA, NDI, Nurick), there is evidence of improvement after surgical intervention in moderate and severe cases of CSM, however, mild cases are less clear ¹⁰. In this regard, the clinical scales suffer from a lack of sensitivity.

Critical Need. For all three areas – diagnosis, differential diagnosis, functional tracking in treatment – objective, empirical measures of dysfunction sensitive to severity of CSM have the potential to enhance rehabilitation of CSM in veterans.

Static balance and CSM. One area with a high potential to advance sensitivity, selectivity and gradations of CSM is a measure of static balance. Balance is the ability to maintain stable postural sway that does not exceed the limits of stability. Balance arises through the integration of sensory (somatosensory, vestibular, and visual inputs) and motor components (flexors, extensors). Sway, measured through center of pressure (COP), is a necessary component of posture as well as a well-established metric of postural control. Excessive sway is a sign of instability which may arise through sensory disturbances, motor dysfunction, or environmental perturbations.

Disturbances of postural control are hallmarks of CSM ²² and are a consequence of abnormalities in proprioception due to dorsal column or spinocerebellar tract damage of the spine ²³ or postural commands to motor neurons ^{24, 25}. Those presenting to the emergency room for head trauma from falling were more likely to have CSM ²⁶. Similarly, those hospitalized for hip fracture were more likely to also have evidence of CSM than similarly aged individuals having elective hip arthroplasty ²⁷. Further, CSM increases the risk of subsequent injury after hip replacement ²⁸. Early detection could serve to decrease rates of injury and compound injury.

Nardone et al. ²⁴ studied body sway of patients with severe CSM and cervical spondylosis without myelopathy using a force platform under conditions of eyes open or closed on a level firm surface compared to healthy controls. COP sway area was greater in both clinical groups under both eyes open and eyes closed conditions, suggesting disturbances of ascending proprioceptive input and impaired

descending motor control. Further, they found substantially greater COP sway area in CSM patients in the eyes closed than eyes open conditions, demonstrating the dependency on visual input for balance in CSM. Yoshikawa et al. ²⁹ also observed that individuals with CSM presented larger COP sway than the less severe CSM, however, there was not supporting MRI or CT abnormalities presented to confirm CSM or its severity. Freppel et al. ³⁰ found COP sway differences between patients with herniated disc and CSM suggesting that while symptom reporting was similar, posturography is sensitive to etiology (acute vs chronic degenerative disease). Thus, the assessment of static balance has considerable promise in providing an objective measure of dysfunction in CSM and contributing to differential diagnosis. Further, evaluating proprioception using posturography may also help to predict surgical outcomes. Takayama et al. observed that early proprioceptive recovery was associated with better functional outcome 2 years after surgery for cervical myelopathy ²². Despite these promising findings, there has not been a study of posturography in veterans with CSM.

The Virtual Environment TBI Screen (VETS) is a new construct that has been validated for evaluating postural control processes. Building on established parameters, the VETS assesses posturography through easily accessible and relatively low cost technology. Currently, a Wii Balance Board (WBB – Nintendo, Kyoto, Japan) ^{31, 32} provides a surface for testing and stabilometers for transducing COP sway area. Virtual reality technology is used to simulate movement using a commercially available large screen television. There are three conditions (eyes open, eyes closed, and watching a dynamic visual scene) repeated on a firm surface or a foam surface. These 6 conditions allow for an assessment of generalized vs specific deficits in COP sway area considering proprioception (firm vs foam surface), dependence of visual input (eyes open vs eyes closed) and visuo-proprioceptive integration (static vs dynamic visual scene) (see Figure 1). The VETS device was specifically designed to be low cost (all components are commercial off-the-shelf) and easily assembled. The user interface was designed to be accessible to novice, but attentive providers. Algorithms are included to provide easily understandable measures among the six conditions. As a clinical device, further development is necessary.

Although we have yet to examine posturography in veterans with CSM, [name] and [name] have active collaborations to study posturography in active duty military (*Military Medicine* in press) and veterans. We are currently conducting a study of posturography at the Syracuse Veterans Affairs Medical Center (SVAMC) in veterans as a function of lifetime mild traumatic brain injury (mTBI) and posttraumatic stress disorder (PTSD). In the interim between initial submission and revision, two veterans with MS volunteered for the study. Although the study has a different focus, the data illustrates the sensitivity of the VETS to subtle differences in balance. No veteran in the study to date has registered a self-reported problem with balance. Figure 2 depicts COP sway for otherwise **HEALTHY** (N = 10), lifetime mTBI (N = 7) and MS (N = 2) veterans under the six conditions. In observing the otherwise **HEALTHY** veterans (open bars), one can see that the foam condition places a substantial burden on balance compared to firm conditions. Further, eyes closed conditions exacerbate COP sway area, especially on foam. One can also see that the ranges of COP sway area in normal

VETS device - Six postural test conditions

Figure 1. VETS - a VR-based balance assessment device tests six conditions. Top row shows the firm support conditions and the bottom row shows the unstable (foam) support conditions. From left to right, the three columns are eyes-open (EO) while viewing a static visual scene, eyes-closed (EC) in front of a dark screen, and EO viewing a dynamic rotating screen.

[figure not shown]

Figure 2. Comparison of VETS COP sway area in SVAMC veterans as a function of history of mTBI and MS. Legend is contained in the figure. The visual conditions were eyes open (EO), eyes closed (EC) and viewing a dynamically rotating science (DYN). These visual conditions were as on Firm and Foam surface. Veterans with lifetime history of mTBI exhibited greater COP sway area during the DYN-FOAM condition compared to HEALTHY veterans. MS veterans displayed greater COP sway area during the EC conditions, and the DYN-FOAM condition compared to HEALTHY veterans.

HEALTHY veterans provide substantial room to detect abnormalities. It is against this background that we will be assessing balance disturbances in CSM.

For the purposes of illustration we compared the two MS veterans to HEALTHY veterans with a $2 \times 3 \times 2$ (Surface x Visual Condition x Clinical Group) mixed model analysis of variance (ANOVA) which yielded a significant triple interaction, $F(2,16) = 5.49, p = .014$. Specific comparisons between conditions showed the two eyes open conditions are similar to HEALTHY veterans ($p > .05$) suggesting for these MS veterans postural control motor outputs are normal. Differences were apparent in the EC conditions suggesting visual input is necessary to maintain balance. Further, the DYN-FOAM condition was compromised in the two MS veterans ($p < .05$), suggesting impaired ability to integrate visual, proprioceptive, and vestibular stimuli in MS. Comparison was also made between those with lifetime history of mTBI and HEALTHY veterans with a similar $2 \times 3 \times 2$ (Surface x Visual Condition x Clinical Group) mixed model ANOVA. The triple interaction was significant, $F(1.176, 17.645) = 5.385, p = .028$ (Greenhouse-Geisser correction for violations of sphericity). Those with lifetime history of mTBI exhibit balance difficulties specifically on the DYN-FOAM condition ($p < .05$). For MS and lifetime mTBI, balance was compromised during the DYN-FOAM condition, which is designed to produce to rollvection³³, that is, perceived self-motion due to conflicting visual, proprioceptive and vestibular inputs.

The ongoing research in veterans demonstrates the utility of the six conditions comprising VETS to expose motor, proprioceptive, vestibular, and integrative sensory deficits. The combination of conditions in VETS provide a means to advance research in CSM beyond that already conducted in civilians to date.

Imposition of posturography is envisioned to aid in clinical assessment in CSM in three meaningful ways: a) assessment of CSM severity, especially in cases of 'mild' CSM, b) differentiating CSM from other entities, c) providing an objective target to assess treatments interventions and recovery. For differential diagnosis, the conditions potentially distinguished by posturography are trauma, ALS³⁴, MS (Figure 2), syringomyelia, myelitis, and vitamin B12 deficiency³⁵ (See Table 1).

Table 1. Sensory Motor Deficits and Expected Impact to Posturography with VETS			
Motor	Proprioception	VETS Conditions	
CSM	?	?	EC, FOAM
Trauma	↓↓	↓↓	ALL
ALS	↓↓	Late Stages	ALL
MS	Late stages	↓↓	EC, DYN-FOAM
Syringomyelia	↓↓	Late Stages	ALL
Myelitis	varied	varied	
Vitamin B12 Deficiency	-	↓	Normal EC

3.0 Objectives

AIM 1A: Determine whether and to what degree balance is altered in CSM. The degree of COP sway will be compared between CSM and controls in the six conditions comprising VETS testing.

Hypothesis 1: Impaired proprioceptive transmission in CSM will result in poorer balance (larger COP sway area) during EC conditions (eliminating the ability to compensate with visual feedback) and FOAM (reducing the reliability of somatosensory feedback) conditions compared to healthy veterans.

AIM 1B: Determine whether VETS enhances sensitivity and selectivity in the diagnosis of CSM. Composite measures of balance will be related to clinical assessment tools and their relationship with MRI.

Hypothesis 2: VETS will provide additional sensitivity and selectivity in identifying CSM compared to current clinical assessment tools.

Hypothesis 3: The degree of COP sway area during EC and FOAM conditions is expected to directly relate to the degree of spinal cord compression quantified from MRI, leading to a more sensitive gradation in the severity of CSM.

AIM 2: Evaluate the VETS scores after surgery for CSM. The degree of COP sway area under the 6 conditions will be compared before surgery, 2 weeks, 6 weeks, and 6 months after surgery.

Hypothesis 4: We expect surgery to reduce COP sway in EC conditions

4.0 Resources and Personnel

All research activities will be conducted at the Syracuse VA Medical Center, using equipment already owned by the PI. All research activities and data storage will take place in the D-wing of the SVAMC. Potentially eligible CSM patients will be identified by Drs. [name], [name], and [name] during CSM surgery scheduling and referred to the study coordinator. Interested patients will be screened additionally and scheduled for an appointment if they are eligible. The study coordinator will consent the participants and obtain HIPAA authorization before collecting study data. Collecting study data will involve administering questionnaires and VETS testing. Drs. [name] and [name] will complete the clinical scales being used in the study. [name] will process VETS data and [name] will run all statistical analyses.

5.0 Study Procedures

5.1 Study Design

For AIM 1, a cross-sectional design that includes within-subjects (VETS conditions) and between-subjects (veteran groups) factors will be used to compare balance and posture in patients awaiting surgery for CSM ($n = 20$) to a cohort of age and gender-matched non-CSM controls ($n = 20$). The 20 veterans with CSM recruited for AIM 1 will also serve as the sample for AIM 2, which is a longitudinal assessment of balance following surgical intervention for CSM. The data generated from the proposed study will provide a base estimate of the variance in our veteran groups for use in the power calculation for a larger follow up study

Veteran volunteers (CSM and control) meeting eligibility criteria will complete one session of VETS balance testing. Those veterans awaiting surgery for CSM will be asked to return for three additional sessions of VETS at designated time points scheduled 2 weeks, 6 weeks, and 6 months post-surgery. For returning CSM veterans, self-report measures will be collected at each additional time point to compare objective (VETS) and subjective (scale measures) assessments of functional impairment related to CSM following surgery. None of the procedures involved in this research project will alter standard of care associated with CSM or the surgical treatment. “Each patient will be cleared by one of the study doctors ([name], [name], or [name]) before participating in the post-surgery sessions. In the event that a patient is found to be physically incapable of safely participating in the first post-surgery session, they will not continue participation in the study until they are cleared by the study doctors. Thus, even if a patient is not cleared to participate in the two week post-surgery time point, they may be cleared to participate in the remaining two sessions (six weeks and six months post-surgery).”

Risks/Benefits of Participation

There are no risks associated with the questionnaires included in this study, as they ask only about physical symptoms and functioning associated with CSM. Although some emotional health questions will be included, they are not expected to be upsetting in any capacity.

The risks associated with VETS testing are minimal and are as follows:

- Discomfort from standing on the WBB or foam for a prolonged period of time
- Dizziness or disorientation when viewing the dynamic condition

These risks will be minimized by allowing participants to step off the WBB/foam between trials if the participant indicates any sign of discomfort. If a participant feels unable to continue with the testing, they will be allowed to cease participation at any time. All participants will be advised to step off the balance board if they feel too dizzy, to minimize fall risk. Additionally, the experimenter overseeing the VETS testing will be trained to spot participants to guard against falls.

We do not expect the inclusion of patients with both CSM and an additional diagnosis (i.e. neuropathy or lumbar spine disease) to alter the risk profile for the study, as each patient will be screened by study clinicians before being allowed to participate in the study. Any patient who is not found physically capable of completing the study assessments will not be informed of the study.

Participants will receive no direct benefit as a result of participating in this study. However, developing the VETS assessment as an objective marker of balance dysfunction in CSM will benefit veterans in the future who are being diagnosed, treated, and rehabilitated for CSM.

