Demographics: The demographics form will ask about basic information, including: age, sex, history of head injury, and current medications.

VETS. Postural stability will be assessed with the VETS system devised by [name] ^{31, 38-40}. All postural conditions are performed in a darkened room. The physical set-up has the front edge of the Wii balance board (WBB) placed at a distance of 40 cm from a 60" commercially-available flat screen television. This device employs a custom-designed software user interface that allows wireless Bluetooth collection of

center-of-pressure data at 100 Hz with high test-retest reliability and immediate display of results. Excellent concurrent validity was determined by comparing VETS with a research grade gold-standard NeuroCom, which revealed $ICC > 0.90$ (min: 0.901, max: 0.995, $p < 0.01$).

The postural stability task will involve six conditions during which veterans are instructed to look straight ahead and maintain an upright stance as stably as possible (see Figure 2). Veterans are barefooted with feet comfortably placed ~25 cm apart. The six conditions are (1) Eyes Open (EO) Firm – eyes open with stable support surface (i.e. WBB) and static visual scene, (2) Eyes Closed (EC) Firm – eyes closed with stable support surface and dark screen, (3) Dynamic Scene (DYN) Firm – eyes open with a stable support surface while viewing a scene dynamically rotating in the roll (fronto-parallel) plane at 60 deg/s, (4) EO Foam - eyes open with unstable support (Airex foam pad placed on top of the WBB) and stable visual scene, (5) EC Foam – eyes closed with unstable support and dark screen, and (6) DYN Foam – eyes open with unstable support and rotating scene. Each condition lasts 30 secs and is repeated 3 times before progressing to the next condition. The conditions are tested in order 1-6, in a manner that emulates the validated Sensory Organization Test (SOT) protocol (Natus/Neurocom). For safety, an experimenter guards the veteran to protect against falls.

B. Procedure

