All statistical analyses will be performed using IBM SPSS Statistics Version 24 and MedCalc. For descriptive purposes, continuous data will be summarized with the number of non-missing values, mean, and standard deviation, minimum, median, and maximum and categorical data will be summarized with the number of non-missing values and the numbers (frequencies) of values equal to each of the possible categories, unless stated otherwise. Univariate analyses will examine data distributions, potential outliers and missing data. All statistical tests will be two-sided with a significance level of alpha=0.05. Unless otherwise stated, no multiplicity adjustment will be applied and no missing values will be imputed. For analysis of posturography data, each of the six VETS postural conditions (see Figure 2) will be tested three times for each participant from which an average is calculated for each condition. These within-subject, within-condition averages will be used in model building to assess between groups differences in balance (AIM 1a) and within-groups change in balance over time following surgical intervention (AIM 2).

For **AIM 1a**, mixed model ANOVA will be used to compare veteran group (CSM vs Control) and within-subject visual (EO, EC, and DYN) and surface conditions (FIRM and FOAM). Average COP sway, COP velocity, and MSE of COP sway velocity for each of the six VETS conditions will serve as dependent measures in separate models. Using Mauchly's tests, violations of sphericity will be detected, are corrected with Greenhouse-Geisser adjustments.

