6.0 Reporting

Adverse Event (AE): If a research participant exhibits acute discomfort as noted by the researcher during a testing session (e.g., expressing discomfort or overwhelming disorientation while standing on the VETS apparatus), they will be asked if they feel they are able to carry on with the session and offered a break. If they are unable to carry on, the PI will be informed immediately and the testing session will be terminated for the day.

Serious Adverse Event (SAE): An example of a SAE would be a participant suffering severe complications associated with the CSM surgical treatment. It is likely that such complications will occur only unrelatedly to any study activities—especially if a participant is prohibited from active participation while experiencing such complications. In the event that a participant has a strongly negative response to the surgery, the participant will not be scheduled for any post-surgical appointments.

An AE temporally related to participation in the study will be documented whether or not considered related to the test article or procedure. This definition includes current illnesses and injuries and exacerbations of preexisting conditions including changes to psychological state. AE will be kept in the subject tracking log and reported as a summary at continuing review. Expected adverse events which are not serious are reported on the Continuing Review Progress Report (CR). Any unanticipated adverse event related to application of tDCS will be reported to the IRB within 10 days, as per Federal Regulations Title 21 812.150 (1).

SAE, such as hospitalization for more than 24 hours, will be reported to the IRB within 5 days per SOP 151-17. This will be accomplished by submitting an adverse event report to the IRB.

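### Section 5.6 has no rule for stopped trials or empty conditions, which can bias the Aim 1A group comparison, mainly on foam

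*Combined protocol and SAP*

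**What the plan says.** Section 5.1 (Risks/Benefits) allows testing to be interrupted in two ways. "All participants will be advised to step off the balance board if they feel too dizzy". Also: "If a participant feels unable to continue with the testing, they will be allowed to cease participation at any time". Section 6.0 adds that if a participant cannot carry on, "the PI will be informed immediately and the testing session will be terminated for the day". The dizziness risk is listed in 5.1 as "Dizziness or disorientation when viewing the dynamic condition".

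Section 5.5 fixes the test sequence: "Each condition lasts 30 secs and is repeated 3 times before progressing to the next condition", and "The conditions are tested in order 1-6". Conditions 4 to 6 are the foam conditions.

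Section 5.6 says each condition "will be tested three times for each participant from which an average is calculated for each condition", and that "no missing values will be imputed" unless otherwise stated. Aim 1A is analysed by a mixed model ANOVA (group by visual condition by surface) with Mauchly's test and the Greenhouse-Geisser correction. The primary measure is COP sway area. Hypothesis 1 (section 3.0) predicts larger sway in CSM under eyes-closed (EC) and foam conditions.

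No section says whether a trial that ends before 30 seconds is repeated, kept as a short record, scored as a failure or discarded. None says how many trials an average needs, or what happens to a participant with no valid trial in a condition.

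**The concern.** The outcome is instability, and a trial may stop because the participant became unstable or disoriented. Missing trials may then carry information about the outcome, and under Hypothesis 1 they would be more frequent in CSM. Discarding them would remove some of the poorest performances from the group expected to perform worst.

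The fixed order adds to this, because a session that ends early loses foam data first and foam is half of Hypothesis 1. In the ANOVA form that section 5.6 describes, one empty condition then costs the participant's data in all six. With 20 per group, each patient lost is 5% of the CSM arm. Section 5.1 says the data will supply variance estimates for powering a larger study, so selective loss would carry forward.

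**Working it through.** **1. Layout.** 6 conditions × 3 trials = 18 trials. Foam is trials 10 to 18. A session that ends before trial 10 and is not completed later has no foam data.

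**2. Effect of an empty condition.** Mauchly's test and the Greenhouse-Geisser correction belong to the conventional repeated-measures ANOVA, which needs all six condition means per participant. Complete-case deletion is an inference from that method. The plan does not state it.

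**3. Plan's own figures.** There are none to reproduce. The documents give no effect size, SD, power or stop rate, so every input below is an assumption. Each calculation covers a two-group comparison in one condition, not the full factorial model.

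**4. Probabilistic link.** Log sway has single-trial SD 1, true shift 0.80, three trials, and trial ICC 0.5 or 0.8. The stop probability is logistic in that trial's sway, with the same function in both groups. Estimated difference by share of CSM trials stopped:

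| Rule and link to sway | 5% | 10% | 20% |
|---|---|---|---|
| Stopped trials discarded, no link | 0.80 | 0.80 | 0.80 |
| Discarded, moderate link (slope 1) | 0.78–0.80 | 0.78 | 0.75–0.77 |
| Discarded, strong link (slope 2.5) | 0.76–0.78 | 0.73–0.75 | 0.66–0.69 |
| Any stop empties the condition, strong link | 0.69–0.70 | 0.62–0.64 | 0.54–0.56 |

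- Largest shrinkage from discarding: 1 − 0.662/0.80 = 17%.
- At that extreme (20%, strong link), power falls from 87% to 81% (ICC 0.5) or from 77% to 71% (ICC 0.8), and 3% to 5% of CSM patients have no value in the condition.
- If any stop empties the condition, power at the same extreme is 57% or 47%.
- If stopped trials are kept with the step-off excursion in the record (+0.7 log), linked stops give 0.81 to 0.89, so the difference grows.
- If they are kept but truncated (−0.3 log), the result is 0.76 to 0.80.

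**5. Strict threshold.** Log sway has between-subject SD 0.5, trial SD 0.35 and true ratio 1.5. Every trial above a fixed sway level stops, and no other trial does.

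- Total SD = √(0.25 + 0.1225) = 0.610. Shift = ln 1.5 = 0.405, and 0.405/0.610 = 0.664 SD.
- Threshold at the control 95th percentile (5% of control trials stop): CSM share = 1 − Φ(1.645 − 0.664) = 16%.
- Threshold at the control 90th percentile (10% of control trials stop): CSM share = 1 − Φ(1.282 − 0.664) = 27%.
- Simulated ratios with stopped trials discarded: 1.37 and 1.30. Log-scale shrinkage: 1 − 0.315/0.405 = 22%, and 1 − 0.262/0.405 = 35%.
- Power with all trials: SD of a three-trial mean = √(0.25 + 0.1225/3) = 0.539, so d = 0.405/0.539 = 0.75. The two-sided 5% t test with 20 per group then has 64% power.
- Power with stopped trials discarded: about 57% and 48%. With stopped trials ranked worst: about 63% and 60%. These simulated figures carry an error of one to two points.
- In the 27% case, about 12% of CSM patients have no value.

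**6. Same SDs, softer link.** With a logistic link the ratio at 16% stopped is 1.47 (slope 1 per SD) or 1.42 (slope 2.5). At 27% it is 1.45 or 1.37. With no link it stays at 1.50. The strength of the link therefore matters as much as the stop rate.

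**The case against.** The strongest reply is that the plan states no rule of averaging completed trials only. A reader might infer one from the averaging sentence and the no-imputation sentence, but repeating the trial, keeping the short record or scoring it would fit the text equally well. The direction of bias is then open, since keeping the step-off excursion can inflate the difference. This stands, and it is why the point concerns a missing rule with a conditional consequence.

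The mechanism also needs limits. The step-off instruction concerns dizziness, which section 5.1 ties to the dynamic scene. It does not mention loss of balance, and the documents address falls only through guarding. Section 5.4 requires CSM patients to stand unsupported with eyes closed for at least 30 seconds, the length of a trial. It also excludes anyone who cannot stand feet together with eyes closed, while testing uses a wider stance. Section 5.1 screens out patients not physically capable of the assessments, and 6.0 offers breaks. A reader might infer that all EC and foam comparisons are equally exposed. The documents do not support that. EC-Firm is little exposed, DYN-Foam is the most plausible path, and EC-Foam is possible because eligibility does not test standing on foam. These safeguards also leave stop rates of 16% to 27% unsupported by anything in the plan.

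A reader might further infer that improvement after surgery is hidden in Aim 2. That does not follow, because stops at the post-surgery visits would act in the opposite direction and nothing in the documents says which would dominate.

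Finally, this is a pilot, and 5.6 says missing data will be examined. Examining missing data does not settle how a stopped trial is scored.

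**Conclusion.** The point holds as a conditional one and should be addressed. The plan foresees stopped trials and ended sessions, tests foam last, and has no scoring rule, minimum number of trials or method that retains a participant with an empty condition.

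Bias towards the null requires two things together: stopped trials are discarded, and stops are likelier at high sway. With both, shrinkage is about 0% to 17% under a probabilistic link with 5% to 20% of CSM trials stopped. It is about 22% under the strong link at 27% stopped (ratio 1.37 against 1.5). The strict threshold gives ratios of 1.37 and 1.30, which is an upper-end case because the sway-stop link is deterministic. If stops are unrelated to sway there is no bias, only lost precision. Emptying a whole condition after any single stop costs more than averaging the remaining trials. Confidence is medium, because stop rates and link strength are assumed throughout.

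**What to change.** The safety instructions are not in question. The changes concern recording and analysis.

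- Record each of the 18 trials as completed, stopped (reason: loss of balance, dizziness, discomfort, other) or not attempted.
- State in 5.6 how a stopped trial is scored and the minimum number of trials per average. Report stops by group and condition.
- Fit Aim 1A with a linear mixed model that keeps participants who have an empty condition. This prevents the loss of their other data, but it does not by itself remove bias when stopping depends on the unobserved sway.
- For that reason, add a prespecified rank-based sensitivity analysis for the EC and foam comparisons. Trials stopped for loss of balance or dizziness rank worst, with participants ordered by number of such stops and then by sway in completed trials. Not-attempted trials and stops for other reasons are treated as missing, so that discomfort or an early end is not scored as poor balance.

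The cost is one data field per trial and one extra analysis. The rank analysis gives no sway ratio, so it sits beside the main estimate. It also leaves foam trials never reached as missing, so their counts by group should be shown with it.
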